6.1.3 Re-screening of Subjects

Re-screening will be allowed for subjects who screen fail after approval by the Medical Monitor. A subject may only be re-screened one time.

To re-screen a subject:

- The Medical Monitor must be contacted for re-screening approval
- The subject's legally authorized representative must be re-consented and assent (if required) must be re-obtained
- The subject must receive a new subject identification number assigned by IWRS.
- All screening evaluations must be repeated (see Section 6.1)
- All inclusion and exclusion criteria must be met (see Section 4)

6.2 Treatment Period

6.2.1 Day 1 Visit (Baseline)

The following baseline assessments will be performed for subjects who meet all eligibility criteria (Section 6.1, Appendix A):

- Subject's visit registration in IWRS
- Central laboratory tests (see Appendix C):
 - Serum potassium
 - Serum chemistry
 - Plasma parathyroid hormone
 - Serum fluoride
 - Urinalysis (not required for anuric subjects, see section 7.2)
 - Hematology (CBC)
 - Local urine and central serum pregnancy test (female subjects of child-bearing potential only)
- Patiromer dispensation, administration (if possible based on individualized administration time as described in Section 5.5; first dose only)
- Patiromer palatability assessments for subjects ≥ 6 years of age who consume patiromer at the site
- Train parents or representative and, if applicable, subjects on patiromer dosing (including preparation, accountability and compliance)
- Provide parents or representative and, if applicable, subjects with study materials (i.e., Subject Dosing Diary, dosing instructions and emergency card)
- Assessment of AEs
- Assessment of concomitant medications
- Next visit scheduling

6.2.2 Day 3 Visit

Patiromer dose may be adjusted on the Day 3 Visit based on the potassium level measured locally according to the titration algorithm. A description of the patiromer dose titration algorithm is provided in Section 5.2.1.

At the discretion of the Investigator, the Day 3 Visit is optional for subjects whose most recent Screening local K^+ is < 5.5 mEq/L.

The Day 3 Visit is mandatory for subjects whose most recent Screening local K^+ is ≥ 5.5 mEq/L.

The activities for Day 3 (± 1 day) are detailed below and in Appendix A:

- Subject's visit registration in IWRS
- Vital Signs (resting heart rate and sitting BP)
- 12-Lead ECG (Only if local K^+ is > 6.0 mEq)

- Blood or serum potassium levels (measured locally) and serum potassium measured by central laboratory
- Patiromer dose down titration if needed (see Section 5.2.1)
Note: Patiromer dose up titration may occur only if the K⁺ level is ≥ 5.5 mEq/L and greater than the most recent locally obtained screening potassium value
- Patiromer dispensation, reconciliation, accountability, compliance, and subject retraining (as applicable)
- Review of Subject Dosing Diary by Investigator and/or designee
- Assessment of AEs
- Assessment of concomitant medications
- Next visit scheduling

6.2.3 Day 7 Visit

Patiromer dose may be adjusted on Day 7 based on the potassium level measured locally according to the titration algorithm. A description of the patiromer dose titration algorithm is provided in Section 5.2.1.

The activities for Day 7 (± 3 days) are detailed below and in Appendix A:

- Subject's visit registration in IWRS
- Vital Signs (resting heart rate and sitting BP)
- 12-Lead ECG (Only if local K⁺ is > 6.0 mEq)
- Blood or serum potassium levels (measured locally) and serum potassium measured by central laboratory
- Serum chemistry (measured by central laboratory)
- Patiromer dose titration (if needed), dispensation, reconciliation, accountability, compliance, and subject retraining (as applicable)
- Review of Subject Dosing Diary by Investigator and/or designee
- Assessment of AEs
- Assessment of concomitant medications
- Next visit scheduling

6.2.4 Day 14 Visit

Patiromer dose may be adjusted at the Week 2 (Day 14) Visit based on the potassium level measured locally according to the titration algorithm. A description of the patiromer dose titration algorithm is provided in Section 5.2.1.

The activities for Day 14 (\pm 3 day) are detailed below and in Appendix A:

- Subject's visit registration in IWRS
- Physical examination
- Body weight and height
- Vital Signs (resting heart rate and sitting BP)
- 12-Lead ECG (Only if local K⁺ is > 6.0 mEq)
- Potassium levels (measured locally and by central laboratory).
- Other central laboratory tests (see Appendix B):
 - Serum chemistry
 - Plasma parathyroid hormone
 - Serum fluoride
 - Urinalysis (not required for anuric subjects, see section 7.2)
 - Hematology (CBC)
- Patiromer dose titration (if needed), dispensation, reconciliation, accountability, compliance, and subject retraining (as applicable)
- Parent's or legally authorized representative's assessment of subject's (< 6 years of age) acceptance of patiromer
- Review of Subject Dosing Diary by Investigator and/or designee
- Assessment of AEs
- Assessment of concomitant medications
- Next visit scheduling

6.2.5 Week 3, Week 5, Week 7, Week 10, Week 14, Week 18, and Week 22 Visits

Patiromer dose may be adjusted at any scheduled visit based on the potassium level measured locally according to the titration algorithm. A description of the patiromer dose titration algorithm is provided in Section 5.2.1. Study visits at Week 3, Week 10 and Week 22 may be omitted under certain circumstances; refer to Section 3.2.3 for details. During the Long-Term Treatment Phase, up to 2 non-sequential study visits may be conducted remotely using the Sponsor approved Home Care vendor at certain investigational sites in certain countries; refer to Section 3.2.3 for details.

The activities for Week 3 (\pm 3 days) and Weeks 5, 7, 10, 14, 18, and 22 (\pm 7 days) are detailed below and in Appendix B:

- Subject's visit registration in IWRS
- Vital Signs (resting heart rate and sitting BP)
- 12-Lead ECG (Only if local K⁺ is > 6.0 mEq)

-
- Physical examination (Week 7 and Week 14 only); may be omitted for Home Care visit
- Body weight and height (Week 7 and Week 14 only); may be omitted for Home Care visit
- Potassium levels (measured locally and by central laboratory); the investigator will review local potassium results within 24 hours for any Home Care visit.
- Other central laboratory tests for Week 7 and Week 14 only (see Appendix B):
 - Serum chemistry
 - Serum fluoride
 - Hematology (CBC)
- Patiromer dose titration (if needed), dispensation, reconciliation, accountability, compliance, and subject retraining (as applicable). For Home Care visits, the investigator will make decisions about patiromer dose titration within 24 hours after the visit; the subject or guardian will be contacted as soon as feasible if the investigator determines that a dose adjustment is required; any dose adjustment will take place at the next administered dose
- Assessment of AEs
- Assessment of concomitant medications
- Next visit scheduling

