4.3 Subject Withdrawal

Within the provisions of informed consent and assent (if required) and good clinical judgment with respect to the subject's safety, every attempt should be made to have subjects complete both Treatment Periods and Follow-up Period. Subjects and subject's legally authorized representatives will be informed that they are free to withdraw from the study at any time. The Investigator and/or the Medical Monitor may exercise his or her medical judgment to terminate a subject's participation in the study because of clinically significant changes in any clinical or laboratory parameter. If the Investigator is concerned regarding any potassium value, a re-test of potassium level and/or ECG evaluation for electrophysiological consequences can be initiated by the Investigator at his/her discretion.

On an ongoing basis, the investigator will monitor the degree of burden of participation in the study as well as the associated risk. Participation in this study should only be continued if the investigator determines there is no more than a minimal increase over the burden and risk that are described in the protocol or associated with routine clinical examinations, clinical care and treatment of patients with chronic kidney disease and hyperkalemia.

All subjects withdrawn early from the study for any reason will be followed for safety for 2 weeks after receiving the last dose of patiomer. Subjects who meet any of the following criteria at any time during the study must be withdrawn from the study and should be medically managed as per standard of care by the Investigator:

- Serum magnesium < 1.0 mg/dL (< 0.41 mmol/L) confirmed by re-test
- Potassium-related ECG changes
- Treatment-related SAE (SAE form must be completed)
- Pregnancy (pregnancy form must be completed)
- Withdrawal of assent by subject (if required) or informed consent by legally authorized representative

Other reasons for withdrawal may include:

- Adverse Event
- Protocol deviation
- Subject's non-compliance: poor compliance with study treatment

- Investigator's decision (e.g., in the Investigator's judgment discontinuation is in the subject's best interest; e.g., need for prohibited medication)
- Subject is lost to follow-up: the subject did not return for visits and study personnel were unable to contact the subject
- Subject transitions to dialysis during the study and does not require additional patiromer treatment (see Section 4.4 for details)

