5.2 Allocation to Treatment

At the Baseline Visit, the IWRS will assign all subjects who meet the entry criteria to their patiromer starting dose. Enrollment will start with the oldest age cohort (age 12 – < 18 years) first, followed by the cohort aged 6 – < 12 years, and subsequently the youngest cohort aged 2 – < 6 years of age. Up to three starting dose levels will be evaluated in each age group. The initial dose evaluated will be the lowest of the planned starting dose levels for each age group.

The planned starting dose levels of patiromer for each age cohort are:

- Age 12 – < 18 years: 4.2 g/day, 8.4 g/day and 16.8 g/day
- Age: 6 – < 12 years: 2 g/day, 4 g/day and 8 g/day
- Age: 2 – < 6 years: 1 g/day, 2 g/day and 4 g/day

Note: the starting doses for the 6 – < 12 years of age and 2 – < 6 years of age cohorts may require modification based upon the DSMC recommendation after their review of the safety and PD data of the older cohorts (see Section 8.6 for further details).

5.2.1 *Patiromer Titration*

Patiromer dose titration is allowed during study visits to achieve and maintain K⁺ levels in the 3.8 – 5.0 mEq/L range. Titrations will be based on potassium levels measured locally and per the protocol-specified algorithm.

Patiromer dose adjustments are planned to be made in increments or decrements that represent the lowest starting dose of patiromer for each age group. Specifically, the following dose adjustments are allowed:

- For subjects Age 12 – < 18 years: titrations up or down by 4.2 g/day
- For subjects Age 6 – < 12 years: titrations up or down by 2 g/day
- For subjects Age 2 – < 6 years: titrations up or down by 1 g/day

[figure not shown]
The DSMC may adjust the titration algorithm for each age cohort after their review of PD and Safety data from the previously enrolled subjects. The maximum dose of patiromer is 25.2 g/day during the study. For subjects in the 2 – < 6 year and 6 – < 12 year age groups the highest anticipated doses are 7 g/day and 14 g/day, respectively; the DSMC may modify these doses for these age groups based on review of safety and PD data (See section 8.6).

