During the 14 Day PD / Dose Finding Phase, patiromer dose up-titration by the permitted titration increment for each age group is allowed beginning at Day 7 for K^+ value > 5.0 mEq/L. Dose titration may not be required if the potassium decrease from the previous visit was ≥ 0.5 mEq/L. Patiromer dose down-titration by the permitted titration decrement for each age group or more is allowed for any K^+ value < 3.8 mEq/L to a minimum patiromer dose of 0 g/day. If patiromer dose requires titration, then initiation of the titrated patiromer dose should occur at the next planned administration.

Day 3 Safety Assessment: As a safety measure to ensure that subject exposure to hyperkalemia is not prolonged, the patiromer dose may be up-titrated at Day 3 only if the K^+ level is ≥ 5.5 mEq/L and is greater than the most recent locally obtained screening potassium value. Note: At the discretion of the Investigator, the Day 3 Visit is optional for subjects whose last screening K^+ is < 5.5 mEq/L; for subjects whose last screening K^+ is ≥ 5.5 mEq/L, the Day 3 Visit is mandatory (see Section 6.2.2).

During the Long-Term Treatment Phase, patiromer dose up-titration by the permitted titration increment for each age group is allowed for any K^+ value > 5.0 mEq/L. Dose titration may not be required if the potassium decrease from the previous visit was ≥ 0.5 mEq/L. Patiromer dose down-titration by the permitted titration decrement for each age group, or more, is allowed for any K^+ value < 3.8 mEq/L to a minimum patiromer dose of 0 g/day. If patiromer dose requires titration, then initiation of the titrated patiromer dose should occur at the next planned administration.

A description of the patiromer dose titration algorithm for each age group is described in Figure 2 below.

Figure 2: Planned Patiromer Dose Titration Algorithm.

^a At Day 3, as a safety measure to ensure that subject exposure to hyperkalemia is not prolonged, patiromer dose may be up-titrated only if the K⁺ level is ≥ 5.5 mEq/L and is greater than the most recent locally obtained screening potassium value. Note: At the discretion of the Investigator, the Day 3 Visit is optional for subjects whose last screening K⁺ is < 5.5 mEq/L; for subjects whose last screening K⁺ is ≥ 5.5 mEq/L, the Day 3 Visit is mandatory (see Section 6.2.2).

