6.5 Other Visits

6.5.1 Safety Visit

Safety Visits are mandatory in certain situations. Mandatory Safety Visits are required within 7 days if subject meets any of the following criteria:

- Local potassium is > 6.0 mEq/L. If the patiromer dose is already at the maximum dose (or anticipated highest dose) for the age group, standard of care for hyperkalemia should be applied including RAASi dose decrease
- Any increase in patiromer dose that is initiated and the next scheduled study visit is > 1 week after the dose increase has been initiated
- Discontinuation per the Investigator's discretion

Note: During the 14-Day PD/Dose finding phase when local potassium measurements > 6.0 mEq/L, the Mandatory Safety Visit is not required if a standard study visit takes place within 3 days, however all listed MSV study procedures must be completed (i.e. ECG) at the standard study visit.

Treatment of these subjects with emergency care for hyperkalemia or prohibited standard of care medications (i.e., sodium polystyrene sulfonate or calcium polystyrene sulfonate) may result in the subject being removed from the study; see Section 5.6 for a complete list of prohibited medications. Investigator must contact the medical monitor to determine if the subject should continue in the study.

The following activities will occur during a Mandatory Safety Visit:

- Subject's visit registration in IWRS
- Vital Signs (resting heart rate and sitting BP)
- 12-Lead ECG if the current or most recent local potassium is > 6.0 mEq/L
- Potassium levels (measured locally and by central laboratory)
- Patiromer dose titration (if needed), dispensation, reconciliation, accountability, compliance, and subject retraining (as applicable)
- Assessment of AEs
- Assessment of concomitant medications
- Next visit scheduling

An unscheduled visit may occur at the discretion of the Investigator. At an unscheduled visit during any phase of the study, the following activities will be performed:

- Subject's visit registration in IWRS
- Assessment of AEs
- Assessment of concomitant medications

Other study procedures described in the protocol including the assessment of potassium levels (measured locally and by central laboratory) may be conducted at the discretion of the Investigator depending upon the reason for the visit.

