entire 12 – <18 year old age group through Day 14. Similarly, such an evaluation also will occur when the entire 6 – <12 year old group completes Day 14 in order to recommend starting doses for the 2 – <6 year old group.

8.6.2 *Stopping Criteria*

Safety Criteria:

The safety profile of patiomer in children > 2 years of age is expected to be similar to the safety profile of patiomer observed in adults (see Section 1.2).

In addition to the AEs mentioned in

Table 5 (see Section 8.2.3) that will be evaluated by the Investigator based on the descriptions in

Table 5 (see Section 8.2.3), the DSMC will review all other AEs (including SAEs) using standard severity descriptors (mild, moderate and severe) included in the protocol. The DSMC will also review all central laboratory data, including occurrences of serum magnesium and potassium below the lower limit of normal as provided in the laboratory reports (see Section 8.6).

Deaths that are assessed as due to hypokalemia will be assessed as related to the investigational drug. Deaths that are assessed as due to hyperkalemia will be assessed as due to failure of the investigational drug.

Study or Dose Level Stopping Criteria:

- If two subjects experience the same severe GI AEs that in the opinion of the Investigator(s) and SMC **are related to patiomer**, the DSMC will be consulted to review the available safety data and either provide approval to continue dosing for all subjects or make recommendations regarding modification of starting dose and/or titration algorithms within an age group and sequentially in younger age groups by dose category
- If two subjects experience medically similar unexpected SAEs that in the opinion of the Investigator and SMC **are related to patiomer** the DSMC will be consulted to review the available safety data and either provide approval to continue dosing for all subjects or make recommendations regarding modification of starting dose and/or titration algorithms within an age group and sequentially in younger age groups by dose category
- If one subject experiences an unexpected SAE that is confirmed **to be related to patiomer**, no additional subjects in the same age cohort will be started on or up-titrated to the dose level at which the SUSAR occurred

For individual subjects experiencing any unexpected drug-related SAE or AE leading to withdrawal, the SMC will review the event and the DSMC will be notified at an ad hoc basis.

8.6.3 *Frequency of DSMC Meetings*

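### No magnesium is scheduled between Week 14 and Week 26, while the dose can still be raised on potassium alone: a minor safety gap that the existing central sample could close

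*Protocol*

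**What the plan says.** **Where magnesium is measured.** Local magnesium is taken at Screening only. All later values come from the central chemistry panel at the times in Appendices A and B (Protocol 7.2, Appendix C). On treatment after Day 1, these are Day 7, Day 14 and Weeks 7, 14 and 26 (6.2.3 to 6.2.6). For the visits from Week 3 to Week 22, 6.2.5 states: "Other central laboratory tests for Week 7 and Week 14 only (see Appendix B". Week 26 falls on the day after the last dose (5.3.3, 6.2.6).

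**When the dose can rise.** Section 5.2.1: "During the Long-Term Treatment Phase, patiromer dose up-titration by the permitted titration increment for each age group is allowed for any" potassium above 5.0 mEq/L, using local values. The step in the oldest group is "titrations up or down by 4.2 g/day"; in the younger groups it is 2 and 1 g/day.

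**What follows an increase.** Section 6.5.1 requires a Mandatory Safety Visit within 7 days after "Any increase in patiromer dose that is initiated and the next scheduled study visit is > 1 week after the dose increase". Its content is introduced by "The following activities will occur during a Mandatory Safety Visit". The list contains vital signs, a conditional ECG, potassium, further titration if needed, and review of adverse events and medications. Potassium is the only laboratory test, as in the matching columns of Appendices A and B.

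**What depends on a magnesium value.** Section 4.3: "Subjects who meet any of the following criteria at any time during the study must be withdrawn from the study", the first criterion being "Serum magnesium < 1.0 mg/dL (< 0.41 mmol/L) confirmed by re-test". Section 5.5 advises considering supplements when magnesium is low or borderline. Section 8.6.2 adds: "The DSMC will also review all central laboratory data, including occurrences of serum magnesium and potassium below the lower limit of normal".

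**The concern.** Low magnesium is a named risk of this drug: Protocol 1.2 reports about 9% of adults in trials below 1.4 mg/dL. The withdrawal rule, the advice on supplements and the DSMC review can work only on values that have been drawn. From Week 14 until dosing ends none is scheduled, although exposure may be stepped up several times on potassium alone. The visit meant to check safety after an increase does not look at magnesium either. What could be missed is a low value in a child at a time when the dose could still be reduced or stopped.

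**Working it through.** The plan states no figure on this point, so there is none to reproduce. The check is interval arithmetic on the visit schedule.

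**Inputs (Appendices A and B, nominal days).** Day 3 (±1), Day 7, Day 14 and Week 3 = 21 (each ±3); Week 5 = 35, Week 7 = 49, Week 10 = 70, Week 14 = 98, Week 18 = 126, Week 22 = 154, Week 26 = 182 (each ±7). Magnesium: Day 7, Day 14, Weeks 7, 14 and 26.

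**Gaps between scheduled values.**
- Day 7 to Day 14: 14 − 7 = 7 days
- Day 14 to Week 7: 49 − 14 = 35 days
- Week 7 to Week 14: 98 − 49 = 49 days
- Week 14 to Week 26: 182 − 98 = 84 days; with windows 175 − 105 = 70 to 189 − 91 = 98

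The last gap is the longest, at 84/182 = 46% of the schedule.

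**Possible increase within it.** One step at each of Weeks 14, 18 and 22 adds 3 × 4.2 = 12.6, 3 × 2 = 6 or 3 × 1 = 3 g/day by age group. An adolescent on 8.4 g/day could reach 8.4 + 12.6 = 21.0 g/day, below the 25.2 g/day maximum. Further steps at Mandatory Safety Visits would come on top.

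**Wait from an increase to the next magnesium (nominal days).**

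| Increase at | Current plan | First visit of any kind |
|---|---|---|
| Day 3 | 7 − 3 = 4 | 4 (Day 7) |
| Day 7 | 14 − 7 = 7 | 7 (Day 14) |
| Day 14 | 49 − 14 = 35 | 7 (Week 3) |
| Week 3 | 49 − 21 = 28 | within 7 (Mandatory Safety Visit) |
| Week 5 | 49 − 35 = 14 | within 7 (same) |
| Week 7 | 98 − 49 = 49 | within 7 (same) |
| Week 10 | 98 − 70 = 28 | within 7 (same) |
| Week 14 | 182 − 98 = 84 | within 7 (same) |
| Week 18 | 182 − 126 = 56 | within 7 (same) |
| Week 22 | 182 − 154 = 28 | within 7 (same) |

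**Why the test should be tied to the first visit of any kind.** Testing at Mandatory Safety Visits alone would leave holes, because a scheduled visit exactly 7 days ahead is not more than a week away and triggers no such visit.
- Increase at Week 3, and again at a Mandatory Safety Visit on day 28: Week 5 is 35 − 28 = 7 days on. Without a test there, the next value is Week 7, 49 − 28 = 21 days after the increase.
- Increases at Week 7 and at Mandatory Safety Visits on days 56 and 63: Week 10 is 70 − 63 = 7 days on. The next value would be Week 14, 98 − 63 = 35 days.
- Week 3 held on day 24 and Week 5 by day 31: at most 7 days apart. The next value would be Week 7, up to 56 − 24 = 32 days.

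Tying the test to the first visit catches all three, at Week 5, Week 10 and Week 5. The nominal waits can still stretch if that visit is held late in its window. With Day 14 on day 14 and Week 3 on day 24 the wait is 24 − 14 = 10 days, unless the longer interval is itself taken to trigger a Mandatory Safety Visit.

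**Late gap for a subject with no increase.** With Weeks 18 and 22 added: 126 − 98 = 28 days (up to 28 + 14 = 42). If Week 22 is skipped: 182 − 126 = 56 days (up to 56 + 14 = 70).

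**The case against.** The best case for the plan is that monitoring is front-loaded and backed by judgement. Every subject who stays on schedule has four post-dose values by Week 14. Supplements may be considered even for borderline values (5.5). Investigators may add tests at unscheduled visits (6.5.1) and, with the Medical Monitor, may end participation for significant laboratory changes (4.3). The DSMC sees low central values and may change titration (8.6.2, 8.6.3). The Week 26 draw still supplies the end-of-treatment shift table (SAP 7.10.3) and can still prompt supplementation.

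All of this stands and keeps the point minor. It does not remove it. In the interval these safeguards are optional or need a value that nobody is required to draw, and the explicit allowance for more frequent testing in 7.2 covers calcium and phosphate only. The statement in 1.2 that events tended to come early is about gastrointestinal events; no timing is given for magnesium.

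Two stronger readings are tempting and not supported.
- A reader might infer that the schedule contradicts 4.3. It does not: that rule says when a known value must lead to withdrawal and sets no sampling frequency.
- A reader might apply the adult 9% to 36 to 54 subjects (0.09 × 36 = 3.2; 0.09 × 54 = 4.9) and speak of 3 to 5 missed cases. That count covers the whole study and the 1.4 mg/dL threshold, and says nothing about Weeks 14 to 26 or values below 1.0 mg/dL.

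**Conclusion.** The point holds as a minor, inexpensive safety improvement. No magnesium is scheduled for 84 nominal days (70 to 98) in which dosing can still be raised on potassium alone, and Week 14 is the last scheduled value that can alter patiromer dosing. Within that interval 4.3 can act only on optional or Early Termination values. This rests on the visit schedule as written and on no assumed event rate. The documents give no paediatric rate, no timing, no link to dose increases and no rate below 1.0 mg/dL, so the gain in detection cannot be quantified. The primary endpoint is unaffected.

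**What to change.** In Protocol 6.2.5, 6.5.1 and the tables of Appendices A and B (and their copies in the SAP), add magnesium to the central serum sample already sent for potassium at:

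- (a) Week 18, and Week 22 if attended;
- (b) the first visit of any kind, scheduled or Mandatory Safety Visit, after any dose increase, including an increase made at a Mandatory Safety Visit.

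Section 3.2.3 already bars skipping Week 3, Week 10 or Week 22 when the dose was changed at the visit before. For subjects with no increase, the 35-day and 49-day gaps before Week 14 stay as they are, which seems acceptable.

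**Cost.** Part (a) adds at most 2 × 36 = 72 to 2 × 54 = 108 assays, fewer where Week 22 is skipped. Part (b) adds at most one assay per increase, and none where a panel is already due. No extra visit or blood draw is planned, but any value below 1.0 mg/dL needs a repeat draw to confirm it. Whether the existing sample is large enough in young children must be checked in the Laboratory Manual, which is not among the documents.
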